8.7.4 Follow-up of Adverse Events and Serious Adverse Events

All AE will be followed up until the participant has reached one of the endpoints as described here.

- An adverse event that is likely to be related to the product and that persists at the end of the trial, or any SAE occurring after termination of the trial and likely to be related to the product, will be followed up by the investigators until the participant has completely recovered, recovered with sequelae, or died.
- All other AE will be followed up until the participant has completely recovered, or they complete the study.

A thorough investigation will be conducted to determine causality. Adverse events will be recorded in detail during the course of the trial, irrespective of the possible causal relationship with the measles vaccine.

8.7.5 Grading of adverse events

Adverse events will be graded using a specific grading structure for each event type on a 4 level scale from 0 (none) to 3 (severe). These are described in Appendix 3

8.7.6 Classification of association of events with vaccination

The investigator will assess whether any adverse event is related to the immunization using the following scale and according to the following definitions (based on Workbook for Investigators, WHO/TDR).

- Not related: The event is clearly related to other factors such as the patient's clinical state, therapeutic intervention or concomitant therapy.
- Unlikely to be related: The event was most probably produced by other factors such as the patient's clinical state, therapeutic intervention or concomitant therapy, and does not follow a known response pattern to the study vaccine.
- **Possibly related:** The event follows a reasonable temporal sequence from the time of study vaccine administration and/or follows a known pattern to the study vaccine but could have been produced by other factors such as the patient's clinical state, therapeutic intervention or concomitant therapy.
- **Probably related:** The event follows a reasonable temporal sequence from the time of study vaccine administration and/or follows a known response pattern to the study vaccine and could not have been produced by other factors such as the patient's clinical state, therapeutic intervention or concomitant therapy. These events include but are not limited to those that require medical attention and result in withdrawal from follow-up. Any available medical records needed to accurately describe the event will be obtained from the appropriate health care provider.
- **Most probably related:** The event follows a reasonable temporal sequence from the time of vaccine administration; and/or follows a known response pattern to the trial vaccine; and could not have been produced by other factors such as the patient's clinical state, therapeutic intervention or concomitant therapy; and either occurs immediately following trial vaccine administration, or there is positive reaction at the application site.
- **Insufficient data to assess:** There is not enough clinical and/or laboratory information to suggest the relationship between the experience and the trial product.

A report on all **Severe** Adverse Events and all **Serious** adverse events will be submitted to the DSMB within 7 days, following the Terms of Reference of the DSMB for the Measles Aerosol Project (Appendix 2). The DSMB will make the final decision on the classification of serious and severe adverse events.

In addition, the DSMB will receive summary reports of all AE quarterly (see DSMB TORs).

8.8 Measles surveillance in the study area

A surveillance system is to be established (as an entity separate from the trial) in the entire blocks containing the trial areas. It will be established as described in the WHO Best practices for measles surveillance⁴⁹ and in the Field Guide -Measles Surveillance & Outbreak

Investigation Guidelines⁵⁰ (2005) Government of India, Department of Family Welfare New Delhi.

It is expected that this surveillance system will be operational before the start date of the trial.

The primary purpose of measles surveillance will be to detect, in a timely manner, all areas in the trial whether the measles virus is circulating. Surveillance will be undertaken with support from the Immunization Programme of the State of Maharashtra and with the National Polio Surveillance Project in India. The surveillance system will involve the following:

- All the health facilities/health providers in the study area will be trained to implement timely notification of clinically diagnosed measles (probable) cases will be promoted to detect cases and outbreaks. A designated surveillance medical officer (SMO) will conduct monthly active searches in the registry files (outpatient and inpatient records) to ensure all probable measles cases are reported. All measles outbreaks will be serologically confirmed to differentiate them from other fever and rash outbreaks. The surveillance data should be analysed at all levels to determine and improve the immunization strategies.
- In addition, **during the home and clinic visits** the field workers, medical doctors and nurses will solicit information on the presence of cases of rash and fever illness in the household and in the neighbourhood where the infants enrolled in the trial reside. Any probable case will be reported to the designated SMO for it investigation as per the Field Guide -Measles Surveillance & Outbreak Investigation Guidelines.

Every confirmed case of measles (i.e. laboratory or epidemiological confirmation) and any confirmed outbreak in the study area or surrounding areas will be reported within 24 hours to the Principal Investigator by the State of Maharashtra EPI Manager and by the designated SMO. All confirmed measles cases will be managed according to the National guidelines including the administration of Vitamin A.

The designated SMO at each district will collect the surveillance forms (VPD - H002) from all the reporting units, collate them in designated format (VPD - D001 form) and compile the district report. The District Immunization Officer (DIO) will send this routinely every week to the State EPI officer, RC or State SMO by Tuesday of each week. The VPD-D002 form should be used to track completeness and timeliness of reporting from the reporting units. This information should be sent on a quarterly basis by the DIO to the State Programme Officer.

Moreover, the State of Maharashtra will share with the PI investigator monthly updates on the performance of the surveillance systems using the indicators defined in the Field Guide - Measles Surveillance & Outbreak Investigation Guidelines.

The DIO/SMO will analyse the available district/block data on a weekly basis, using and reconciling case information from different surveillance systems to identify outbreaks of measles. As per national guidelines, the presence of measles outbreak should be verified if five or more than five clinically diagnosed cases of measles are identified in a block in a week, or five or more than five confirmed cases of measles occur in an area bordering several blocks in a week, or one or more than one death due to measles occurs in a block in a week.

If possible outbreaks are identified, measles outbreak investigations should be initiated as described in Chapter 5, Measles Outbreak Investigation of the Field Guide -Measles Surveillance & Outbreak Investigation Guidelines. In brief, the DIO and the SMO will oversee that the following actions will take place:

- Identifying the measles outbreaks that need to be investigated and assigning an outbreak number
- Mobilization of Epidemic Response Team (ERT)
- Orientation & planning meeting at the local level
- Conducting measles case search
- Collection and shipment of specimens to the laboratory
- Laboratory confirmation of the outbreak
- Data analysis
- Conversion of data to information for action
- Report writing
- Giving feedback
- Initiating actions including vaccination activities.

8.9 Procedure for monitoring subject compliance

Each subject will be given an appointment card for the next schedule visit to the clinic. If any subjects do not turn up on the scheduled date, the investigator will send the designated field worker to their houses and request them to come to the clinic.

9 Assessment of Immunogenicity

9.1 Primary outcome

Measles seropositivity at day 91 post-vaccination.

Measles seropositive specimens are:

• specimens tested by Enzygnost Anti-measles-virus/IgG (Dade-Behring, Marburg, Germany) enzyme-linked immunosorbent assay with optical density signal ≥ 0.1 , or

specimens tested by Enzygnost with optical density signal < 0.1, that are subsequently tested by plaque reduction neutralization test with a result of \geq 120 mIU/ml measles antibody titre.

For further details, please see Sample processing (HPA 1/1, WHO 2/1, WHO 3/1, WHO 4/1), Measurement of outcomes (SOP HPA 5/1, HPA 6/1, HPA 7/1)

9.2 Secondary outcomes

For all infants:

- Geometric mean titres, pre-vaccination and at day 91;
- Seroconversion (defined as a change from Enzygost OD <0.1 to OD \ge 0.1 or PRNT from <120 to \ge 120 mIU/mL) measured in paired samples from day 0 and day 91;
- As covariates for inclusion in multivariable analyses: age; sex; day 0 antibody titre; study site; crying when vaccine given (aerosol arm only); presence of respiratory tract symptoms at time of vaccination (aerosol arm only). In addition, random subsets of 80 infants each with OD 0.1-0.2 and OD>0.2 at day 91 will be assessed for PRNT antibody concentrations to determine the relationship between PRNT and Enzygost optical densities/concentrations and validate the use of the cut-off of 0.1 for PRNT testing.

For infants in the day 28 blood sample subset or the day 364 blood sample subset:

- Geometric mean titres to describe evolution of antibody response at days 0, 28, 91, 364;
- Seropositivity at 364 days in infants with antibody titre \geq 120 mIU/ml at day 91.

10 Assessment of Safety

10.1 Primary outcome

Adverse events up to and including day 91 post-vaccination.

10.2 Secondary outcomes

• Frequencies of individual adverse events

For further details of assessment and management of adverse events, please see Section 8.7 and SOPs WHO 1/1, WHO2/1, WHO 3/1.

11 Statistics

11.1 Description of statistical methods

A detailed analysis plan will be finalised prior to locking of the database and commencement of statistical analysis.

11.1.1 Analysis sets

- Primary analysis: per protocol (infants receiving the allocated vaccine and available for follow up at 91 days post-vaccination). For non-inferiority hypothesis, this is the conservative analysis;
- Secondary analysis: intent-to-treat analysis (all infants randomized, analysed in the group to which they were allocated, irrespective of intervention received) of primary and secondary outcomes.

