12.1.2 Immunogenicity

Primary analysis is to calculate the 2-sided 95%CI for the difference in proportion seropositive at day 91. If lower limit of difference greater than -5% then conclude non-inferiority. If lower limit of difference greater than 0% then conclude superiority.

Secondary analyses will include calculation of 95% confidence intervals for seropositivity, seroconversion and geometric means as well as multivariable logistic and normal errors regression adjusting for covariates.

Secondary analysis of factors associated with seroconversion/response, including:

- pre-vaccination titre
- Age (9m,10m,11m) (also look at interaction with intervention)
- Sex (also look at interaction with intervention)
- PHC
- Crying when vaccine given? (also look at interaction with intervention).
- (Another factor we considered before was acute respiratory infection)
- Explanatory variables for stratification of safety profile

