When a unique study ID has been confirmed the person clicks the 'Randomization' button. The next screen gives the allocation as either, 'AEROSOL' or 'SUBCUTANEOUS'. The system records, in a separate database, the details of study site, child's names, Subject ID number, allocation, date and time of randomization. The randomization database will be maintained in Access as backend. This database will be maintained at the CDMC and the backup will be maintained at the backup server which is kept at the Pharmacology Department Museum (old name: Booshnam Moses Computing Center) (Refer SOP Randomization, No: 05 / 02).

SOP VEL 1/1:	Statistical Analysis Plan	Page 5 of 61	
September 11, 2012			

7.3 Blinding of Laboratory Staff:

Staff at the study sites and participants' parents will know which treatment has been given. To minimize bias in the assessment of immunogenicity outcomes, laboratory staff will not know the treatment allocation or the order of specimens that they will analyze.

In order to blind laboratory staff to the specimen collection time (day 0, day 28 day 91 or day 364) for the subjects, a single digit random number will be generated and concatenated with the subject ID. This is called the Lab Code. Thus a subject will have a unique Lab Code of 5 digits.

The laboratory will be provided with lists of 22 pairs (day 0 and day 91) of specimen Lab Codes, which will be randomly ordered. Similarly, for the specimens of children who will be followed up at day 28 and day 364, the laboratory will be provided with lists of randomly ordered Lab Codes.

8.0 Sample size:

8.1 Immunogenicity:

The sample size for the primary outcome is determined using the confidence interval (CI) approach, considering where the CI for the treatment effect lies with respect to a pre-specified margin of non-inferiority and the null effect (1).

Total to be enrolled, 2000. This number was based on the following assumptions:

- Significance 2.5%, one sided for non-inferiority, 5% for two sided superiority;
- Non-inferiority margin 5%;
- Power for non-inferiority 90% if true seropositivity is 90% in both arms;
- 20% loss to follow up by day 91, leaving 1600 available for primary analysis.

Sample size for immunogenicity subset:

Those selected for additional testing at day 28 or at day 364 will have ELISA and PRNT test results at these time points as well as at day 0 and 91.

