In Figure 11.1.1 non inferiority has been demonstrated for scenarios 1), 2) and 3) since the lower limit of the 95% CI is above -5%. In addition for scenario 3) superiority has been shown because the lower limit does not include 0%. For scenarios 4) and 5) non-inferiority has not been demonstrated and for scenario 5) aerosol is inferior as the upper limit does not include 0%.

Note: Using the Wilson score method, 95% CI will be calculated using SAS software. (Newcombe 1998, Agresti et al 1998)

11.2 Per-Protocol (PP) Analysis Set:

This is the analysis set that will be used for the primary analysis of efficacy. The PP analysis set includes all children with an interpretable result from the blood sample scheduled for 91 days (-7 to +28 days), and without major protocol deviations. Study participants remain in the study up to until the point at which they drop-out or deviate from the protocol (Protocol section 12.0).

Protocol deviations include:

- Study participant incorrectly entered the study, e.g. did not meet age criteria;
- Study participant should have been withdrawn during study but was not;
- Study participant did not receive the vaccine according to the arm to which he / she was randomized;
- Study participant received the wrong dose of vaccine;
- Study participant received a dose beyond the recommended multi-dose vial policy
- Wrong subject ID randomized
- Wrong Subject ID
- Home Visit and Clinic visit on same date
- Visits outside the window period
- Wrong labelling of the CRF
- Wrong labelling of vials
- Informed consent issue

The assessment of long-term immunogenicity in the subset of participants from Vadu, includes children with an, interpretable result from blood sample scheduled for 364 days (-7 to +28 days), and without major protocol deviations.

11.3 Modified Intention to Treat (ITT) Analysis Set:

The 'intention to treat' analysis will be conducted as a secondary analysis. In a noninferiority trial such as this, the intention to treat analysis is more likely than the perprotocol analysis to give a type I error (falsely claiming non-inferiority) because this kind of analysis tends to minimize differences between the two treatments (1).

The ITT analysis set includes assessments up to 91 days (-7 to +28 days) post-vaccination. All study participants will be included in the group to which they were randomized.

SOP VEL 1/1:	Statistical Analysis Plan	Page 9 of 61
September 11, 2012		

11.4 As Treated Cohort Analysis set:

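### Non-inferiority is decided in the per-protocol set alone on the ground that it is conservative; that is not guaranteed, and the planned as-randomised comparison has no say

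*Supplement*

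**What the plan says.** Protocol 11.1.1 and 12.1.1 make the per-protocol set primary and the intention-to-treat (ITT) set secondary, with the reason "For non-inferiority hypothesis, this is the conservative analysis". Protocol 12.1.2 gives the decision rule: "If lower limit of difference greater than -5% then conclude non-inferiority". It mentions no second set.

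SAP 11.2 says of the per-protocol set: "This is the analysis set that will be used for the primary analysis of efficacy". Membership requires an interpretable day-91 result and no major protocol deviation. A list of deviations follows (wrong dose, a dose outside the multi-dose vial policy, wrong route, identity errors, visit window, labelling, consent and others), but nothing says which are major. SAP 11.3 keeps ITT secondary, arguing that ITT tends to shrink differences and so is more prone to a false claim of non-inferiority.

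Three other places matter:
- Protocol 7.3 takes withdrawn infants out of the analysis, including those withdrawn for a serious adverse event or at the investigator's judgement.
- SAP 9.2 leaves exclusions from the analysis sets to a pre-analysis review. It does not say that the review is blind to arm or serology.
- SAP Table 12.1.3, whose difference decides non-inferiority, is headed as covering all infants and names no analysis set.

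An ITT difference with 95% CI is already planned (SAP Table 12.1.4B).

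**The concern.** Per-protocol is the more cautious choice in a non-inferiority trial when the main departure is infants receiving the other arm's vaccine, because mixing the arms pulls the ITT difference towards zero. It need not be cautious when infants are removed after allocation for reasons that may differ by route and be linked to response. Removing poor responders from the aerosol arm raises that arm's rate and moves the difference towards non-inferiority.

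Allocation is known to site staff and parents here, the two routes are delivered by different procedures, and the exclusion criterion is open-ended. As written, a trial that meets the margin per protocol and misses it as randomised still concludes non-inferiority. That conclusion carries the immunogenicity case for licensure.

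**Working it through.** **Inputs (SAP 8.1).** "Significance 2.5%, one sided for non-inferiority, 5% for two sided superiority"; a margin of 5 points; "Power for non-inferiority 90% if true seropositivity is 90% in both arms"; "Total to be enrolled, 2000"; "20% loss to follow up by day 91, leaving 1600 available for primary analysis". Allocation is 1:1 (protocol 6.3.1.2), which gives 800 analysed per arm. The interval is the Wilson score interval for a difference, after Newcombe (SAP 11.1).

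**The plan's own figure.** n per arm = (1.960 + 1.282)² × (2 × 0.9 × 0.1) / 0.05² = 757. With a continuity correction it is 797 per arm, 1594 in total, and 1594 / 0.8 = 1993 enrolled. This agrees with 1600 and 2000. At 800 per arm, exact enumeration of the Newcombe interval gives 91.3% power at 90% v 90%, and a 2.5% claim rate at 85% v 90%. The plan is sound before any exclusions.

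**Aerosol-only exclusions.** Let the as-randomised truth be 85% v 90%, exactly on the margin. Exclude a share f of the 800 aerosol infants, whose seropositivity is q. The per-protocol aerosol rate is then (0.85 − f·q) / (1 − f). For f = 0.02 and q = 0.5 this is (0.85 − 0.01) / 0.98 = 0.857. The documents give neither f nor q; both are assumptions.

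| f (infants) | q | Per-protocol aerosol rate | Claim rate, per-protocol rule |
|---|---|---|---|
| none | – | 85.0% | 2.5% |
| 1% (8) | 60% | 85.3% | 3.6% |
| 1% (8) | 50% | 85.4% | 4.1% |
| 2% (16) | 60% | 85.5% | 5.0% |
| 2% (16) | 50% | 85.7% | 6.4% |
| 4% (32) | 60% | 86.0% | 9.2% |
| 4% (32) | 50% | 86.5% | 14.2% |

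**The other direction.**
- Excluded infants respond like the rest (q = 85%): 2.5%.
- Excluded aerosol infants respond better (q = 95%, f = 1–5%): 1.2–2.2%.
- The same f (1–4%) and q (50–60%) in both arms: 1.8–2.4%.

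**Requiring both sets.** In 400,000 simulated trials per scenario, keeping the overlap of the two sets and taking the as-randomised set as all infants with a day-91 result, the claim rate is 2.4–2.5% in every aerosol-only row of the table.

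**Power cost at 90% v 90%, with equal shares of deviators in each arm who respond at the same rate.**

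| Deviators per arm | 800 is the per-protocol count: per-protocol alone → both sets | Deviators come out of the 800: per-protocol alone → both sets |
|---|---|---|
| 2% | 91.2% → 90.6% | 90.7% → 90.0% |
| 5% | 91.3% → 90.5% | 89.8% → 88.9% |
| 10% | 91.2% → 90.4% | 88.2% → 87.1% |

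The rule itself costs about 0.7–1.1 points on either base.

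**Two readings in which power is lower.**
- If ITT means all 2000 with missing results counted as seronegative (the protocol's worst case), each arm's expected rate at 20% loss is 0.8 × 0.9 = 72%. ITT power is then 70% and joint power 68%.
- If 90% is the per-protocol rate and excluded aerosol infants are 50% seropositive, joint power is 86%, 78% and 48% at f = 1%, 2% and 5%. In that case the as-randomised difference really is below zero.

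**The case against.** The protocol defines per-protocol as infants who received the allocated vaccine and were available at day 91. Set beside as-randomised infants with a result, that differs mainly by wrong-route infants, for whom the conservatism argument holds. This stands for the protocol's definition. The difficulty enters with the SAP's wider deviation criterion and with protocol 7.3.

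Most listed deviations can occur in either arm, and none is shown to fall on aerosol alone. Crying, struggling or breath-holding during aerosol delivery is recorded and is not a listed exclusion. Laboratory staff are blinded, and day-91 specimens are unblinded only after database lock (protocol 6.8.1). All of this lowers the risk. It does not settle which deviations are major, or whether those deciding on exclusions know the arm.

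The false claims are counted against the as-randomised population. In the scenarios tabulated, the true per-protocol difference lies inside the margin (about −3.5 to −4.8 points), so for the population the plan names as primary those claims are correct. That is fair, and it is why the rates must be described as relative to the as-randomised population.

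A reader might also infer that the randomised comparison goes unexamined. The documents do not support that: an ITT difference with CI is prespecified, best- and worst-case runs are planned, and excluded infants are listed by arm and reason and compared with included infants at baseline. What is absent is any bearing of these on the conclusion.

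**Conclusion.** The point holds in a limited form. The decision rests on the per-protocol set alone, and the reason given for that is not guaranteed under the SAP's exclusion criterion in an open-label trial. Relative to the as-randomised population, the claim rate would be about 4–14% with 1–4% aerosol-only exclusions at 50–60% seropositivity. It would be 2.5% or less with exclusions that are outcome-neutral or similar in both arms.

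Two stronger readings should be resisted. One is that the per-protocol set is anti-conservative here, or that the trial's error rate is 4–14%: the documents give no number, direction or serology of exclusions, so the range shows sensitivity and is not an estimate. The other is that requiring both sets always keeps the stated 90% power: that depends on what the 800 per arm counts and on ITT meaning infants with an observed day-91 result.

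The change is worth making, because it protects the stated error rate at small cost using a table that is already planned.

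**What to change.** 1. Delete the statement that per-protocol is the conservative analysis in protocol 11.1.1 and 12.1.1.
2. In protocol 12.1.2 and SAP 11.1, state that non-inferiority is concluded only if the lower 95% limit exceeds −5% in both the per-protocol set and the as-randomised set of infants with an observed day-91 result, and is not concluded if the two disagree. Keep best- and worst-case imputation as sensitivity analyses outside the rule.
3. In SAP 11.2, list which deviations are major before unblinding, and in SAP 9.2 require that exclusions be decided blind to arm and serology.
4. Name the analysis set for SAP Table 12.1.3.

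The cost is wording plus the power loss shown in the working. No new data or tables are needed. The sponsor should state whether 800 per arm is the per-protocol count, since that determines whether the stated 90% is kept.
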